- **Feasibility and tolerability of the interventions** assessed by enrollment and retention numbers, protocol related adverse events (AE's), and questionnaires assessing satisfaction, quality of life and mood.
- Adherence to interventions assessed both with self-report and with the use of a smartphone application in conjunction with continuous glucose monitoring.

Secondary Outcomes:

- Weight (scale) and body composition (DXA) obtained at baseline (prior to the weight loss intervention), at 12 weeks (following the weight loss intervention), and at a 6mo follow-up time point.
- Physical activity assessed by accelerometry
- Free-living sleep patterns assessed by wrist actigraphy
- Objective (in-laboratory) sleep recording using Compumedics Inc Siesta digital sleep recorders
- Meal timing and energy intake assessed by photographic food records
- Patterns in 24h glucose assessed by continuous glucose monitors over 7 days before and after the weight loss intervention
- Questionnaire based measures of appetite
- HqbA1c and lipids
- Resting metabolic rate and nocturnal energy metabolism by indirect calorimetery

B. Description of Population to be Enrolled:

Inclusion criteria.

- Adult males and females with a BMI of 27-45 kg/m² and weight stable over the previous 6 months;
- Age, 18-50 years old;
- Passing medical and physical screening, and analysis of blood and urine screening samples:
- Typical eating duration >12 hours per day (assessed by questionnaires);
- Own a smartphone
- Reside or work within approximately 30 minutes driving distance of CU-AMC (potential
 participants living outside of this driving distance could be included in the study at the PIs
 discretion).
- For participants in the optional Reproductive Hormone Sub-study: females, age 18-40, with regular menstrual cycles (between 18-40 days).

Exclusion criteria.

- Pregnancy or lactation for women (women who are >6 months postpartum with no plans of becoming pregnant in the next year and who are not currently lactating can be included; oral contraceptives will be allowed if medication has been consistent for the prior 6 months)
- Postmenopausal women (menopausal status will be assessed during the history and physical, with requirement of self-reported regular menstrual cycles for the last year; women who have undergone hysterectomy but with ovaries in place who continue to have regular menstrual symptoms can be included)

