Dietary and Activity Prescriptions. Both groups will focus on caloric restriction to decrease overall EI. Participants will be given a personalized calorie goal based on their measured RMR. If RMR by indirect calorimetry and by Mifflin St-Jeor equation differ by >10%, then the average of the 2 values will be used. This estimated RMR will be reduced by 10% and then rounded to the nearest 100 kcal

Suggested macronutrient content (55% carbohydrates, 15% protein, 30% fat) will be the same for both groups. Participants in the RCD group will not be given any specific instruction regarding timing of food intake. Participants in the RCD+TRF group will be instructed to eat only during a window of 10 hours, starting within 3 hours of waking. They will also be instructed in specific strategies to support TRF including: strategies to deal with hunger outside eating windows, distraction techniques, and choosing a balanced diet/appropriate portions during feeding windows. All participants will be counseled on the importance of PA for weight loss and will receive a recommendation to perform 150 min/wk of PA.

Self-Reported Dietary Adherence, Effort, and Self-Efficacy: At weeks 4, 8 and 12, participants will be asked to rate on a 1-10 Likert scale: 1) how adherent they were to prescribed study diet over the past week, 2) how hard was it to adhere to prescribed study diet over the past week, and 3) how likely they feel they can adhere to prescribed diet for the next month³⁰. These questionnaires will also be administered monthly from month 4 through 9 to determine whether participants have continued to follow their prescribed dietary pattern. In addition, participants will be asked to use the Meal Logger app (Cohorts 1 and 2) or Google Voice at weeks 4 and 8, and monthly between months 4 and 9 in order to objectively assess adherence to the dietary intervention.

Intervention Safety and Tolerability: Participants will be asked to report AEs to study staff as they occur, to be reported to our IRB as per institutional guidelines. We will collect additional parameters to assess tolerability at week 12 and at the 6 month follow up visit. Quality of life (QOL) will be assessed with the RAND-36^{49,50} physical and mental health component summary score. Mood state will be assessed with the Profile of Mood States 2 (POMS-2)⁵¹⁻⁵³. Eating behaviors will be assessed with the Three Factor Eating Questionnaire (TFEQ)⁵⁴.

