Intervention Acceptability: Satisfaction with both the standard RCD and RCD+TRF program intervention will be assessed at week 12 and month 9 with a questionnaire that asks participants to rate on a 1-10 Likert scale how satisfied they were with specific domains of the intervention. The major domains that will be assessed are satisfaction with: 1) ability to adhere to caloric restriction and time restriction (for RCD+TRF group), 2) content of the dietary support curriculum, 3) content of the exercise support curriculum, 4) group meeting frequency and structure, and 5) weight loss achieved to date. Participants will also be asked in open-ended fashion to provide feedback on each domain of the intervention. We will also assess intervention acceptability by comparing the frequency of protocol related AE's, requirement for protocol modification, and attrition between groups.

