Potential Benefits to Study Participation. The potential benefits to an individual participant in the study are not known. Subjects enrolled in this study will potentially benefit by learning information about their health status. Subjects will receive information on test results including body composition, blood glucose profile, sleep, exercise patterns, energy expenditure and metabolic rate and any of the study information they may be interested in. Subjects will also learn information on body weight regulation through their participation. Subjects will also receive some compensation. The potential benefits of the study to the adult population in general could be significant. The study is expected to lead to new data on the relationships between physiological variables relevant to weight regulation and weight regain following weight loss. This information will inform future strategies for the prevention of weight regain. In light of these potential benefits, the risks to subjects are considered acceptable.

D. Description, Risks and Justification of Procedures and Data Collection Tools:

Risks

Extended daily fasting: Subjects will be asked to fast prior to the screening visit for a blood draw and resting metabolic rate measurement. Due to the extra testing procedures, the fasting period may extend beyond a person's habitual overnight fast. In addition, subjects randomized to the TRF + RCD arm of the study will be asked to extend fasting duration to 14 hours/day for 12 weeks. Extended fasting may result in irritability, nausea, light-headedness.

DXA: The DXA (to assess body composition) procedure involves exposure to ionizing radiation. DXA measurements (3 time points during the study for each subject) involve a total effective

radiation exposure that is roughly equivalent to spending 4 days outside in Denver (<50 mrems), or about <1% of the annual allowable exposure for radiation workers. Having trained technician's conduct the DXA scans, thereby reducing the likelihood of needing repeat assessments, minimizes this risk.

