more than minimal risk, we will utilize the services of a volunteer to serve as a Safety Officer at UC. The PIs, COMIRB, and Independent Study Monitors (Safety Officer and CTRC Research Subjects Advocates) will share the primary responsibility for monitoring study data and safety. The DSMP has been developed with the input from the Independent Monitors.

Roles and responsibilities of the Safety Officer (SO). The safety officer will periodically review safety data and judge whether the overall safety of the trial remains acceptable. Any recommendations to alter study conduct will be based on safety not efficacy; hence, there is no cost to the sample size, power, or final alpha level of the analysis. The SO will specifically review all serious adverse events (SAEs) and summary reports of all adverse events. The sponsor and/or applicant may also make recommendations to the SO for additional data review should a concern arise. The SO may recommend a new course of action for a specific treatment group or may suggest other appropriate courses of action to address general study safety issues that may arise. If warranted, the SO may recommend that the protocol be modified, suspended temporarily, or terminated permanently. The SO will meet in an open format with the study team every year to review the study progress.

The SO will review the following data: adverse events, recruitment and enrollment statistics, race and ethnicity statistics, disqualified and excluded individuals, study progress timeline, procedures for data quality control and safety data (e.g. screening labs, enrollment, inclusion and exclusion criteria, adverse events). The data will be "frozen" 2 to 4 weeks before the SO review and the data will be sent to the SO approximately 7 days before the SO review. Based on the review the SO may recommend alterations or changes to the protocol. Meeting minutes will be prepared by the PI of the project and approved by the SO. The minutes will be sent to: CTRC, COMIRB (annually), research team, and NIH (with annual progress report).

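### Among adverse events, only protocol-related ones are compared between arms, with no stated relatedness criteria or masked assessor, so equal event rates could give unequal counts

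*Combined protocol and SAP*

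**What the plan says.** The first primary outcome in IV.A, feasibility and tolerability, is "assessed by enrollment and retention numbers, protocol related adverse events (AE's), and questionnaires assessing satisfaction, quality of life and mood". The Intervention Acceptability paragraph in IV.C adds a between-arm element: "We will also assess intervention acceptability by comparing the frequency of protocol related" adverse events, with protocol modification and attrition compared alongside. These are the only places where adverse events enter a planned outcome or comparison. The Statistical Analysis text in IV.F does not mention them.

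Collection is wider than the comparison. Under Intervention Safety and Tolerability, "Participants will be asked to report AEs to study staff as they occur", with no limit to related events. The Data and Safety Monitoring Plan says: "The SO will specifically review all serious adverse events (SAEs) and summary reports of all adverse events". That is safety oversight and does not provide for a between-arm analysis.

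The section on defining and reporting serious adverse events grades severity by CTCAE. It mentions relatedness only to decide what goes to the IRB. It does not say who judges relatedness or by what criteria.

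On expected symptoms, the Extended daily fasting paragraph under Risks (IV.D) says: "Extended fasting may result in irritability, nausea, light-headedness". That paragraph covers the screening fast of all participants and the daily 14-hour fast asked of RCD+TRF. The behavioral program paragraph in the same section acknowledges adverse effects of diet change or exercise advice for participants generally, and names no symptom.

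**The concern.** Both arms follow the same calorie rule (resting metabolic rate reduced by 10%), which could plausibly cause some of the same complaints as fasting. A participant in RCD+TRF who reports light-headedness has a symptom that the protocol names for an exposure she has every day. A participant in RCD with the same complaint has only the generic diet and exercise statement behind it. Whether each event counts depends on a judgement that the documents neither define nor mask, in a trial where the arms meet separately and no blinding is described.

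Randomisation protects a comparison of all events by arm. Once events are filtered by an opinion formed after allocation, that protection is lost for the filtered count. The error can run either way: RCD+TRF may look less tolerable than it is, or a real excess in one arm may be labelled unrelated and drop out of the comparison. The trial exists to judge whether RCD+TRF is acceptable for a larger study and to refine it, so a distorted comparison could misdirect that refinement.

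**Working it through.** The plan states no adverse-event rate, attribution rate, test or power for this comparison, so there is no figure of its own to reproduce. What follows only shows how far the mechanism can reach.

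**Inputs from the documents.** 60 participants randomised 1:1, so 30 per arm; significance at p<0.05 (taken as two-sided).

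**Assumed inputs.** True proportion of participants with an event: 20, 40 or 60%, the same in both arms. Probability that the event is called related: 80% in RCD+TRF and 80, 60, 40 or 20% in RCD. Test: Fisher's exact, since none is named for adverse events.

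**Formula.** Expected participants with a related event = 30 × true rate × attribution probability. At a 40% true rate:

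- RCD+TRF: 30 × 0.40 × 0.80 = 9.6
- RCD at 80%: 30 × 0.40 × 0.80 = 9.6
- RCD at 60%: 30 × 0.40 × 0.60 = 7.2
- RCD at 40%: 30 × 0.40 × 0.40 = 4.8
- RCD at 20%: 30 × 0.40 × 0.20 = 2.4

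The probability of a false difference is found by enumerating all pairs of binomial counts and summing the probability of those with Fisher p<0.05.

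| True rate, both arms | RCD attribution | Expected related, RCD+TRF vs RCD | P(false difference) |
|---|---|---|---|
| 20% | 80% | 4.8 vs 4.8 | 1.8% |
| 20% | 60% | 4.8 vs 3.6 | 2.6% |
| 20% | 40% | 4.8 vs 2.4 | 6.1% |
| 20% | 20% | 4.8 vs 1.2 | 14.6% |
| 40% | 80% | 9.6 vs 9.6 | 2.6% |
| 40% | 60% | 9.6 vs 7.2 | 6.3% |
| 40% | 40% | 9.6 vs 4.8 | 21.3% |
| 40% | 20% | 9.6 vs 2.4 | 54.0% |
| 60% | 80% | 14.4 vs 14.4 | 2.7% |
| 60% | 60% | 14.4 vs 10.8 | 10.0% |
| 60% | 40% | 14.4 vs 7.2 | 38.8% |
| 60% | 20% | 14.4 vs 3.6 | 82.9% |

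Comparing all events regardless of attribution, the probability is 2.2% at a 20% true rate and 2.6% at 40% and 60%. Swapping 80% and 20% between the arms gives the same probabilities with the direction reversed.

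With equal attribution there is no bias. The plan contains nothing that secures equal attribution.

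**The case against.** The strongest reply is that adverse events are a small part of the assessment. A reader might infer that tolerability rests on related events alone. It does not. Retention, attrition, protocol modification, satisfaction, quality of life and mood also count, and the tolerability paragraph adds: "We will collect additional parameters to assess tolerability at week 12 and at the 6 month follow up visit". None of the questionnaires needs a causality call, and the mood measure may pick up irritability. This stands, and it confines the point to the adverse-event component. It does not repair that component, because nausea and light-headedness are not the stated target of any questionnaire.

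A reader might also infer that unblinded staff make the relatedness call. The documents name no assessor; they say only that events are reported to study staff. The inference is reasonable without blinding, but what the documents establish is the absence of criteria and of a masked assessor.

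Nor do the documents show that an RCD complaint would be called incidental. The filter is relation to the protocol, not to fasting. Calorie restriction is part of the protocol in RCD, the generic diet and exercise risk covers both arms, and the fasting paragraph also covers everyone's screening fast. Unequal attribution is therefore possible, not demonstrated.

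Finally, no stated decision turns on the related-event count. The criteria for modifying the intervention in IV.F concern recruitment, retention and timing of assessments. Events judged unrelated still reach the Safety Officer in summary. Both facts limit the consequences. Neither supplies an unfiltered comparison by arm.

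**Conclusion.** The point holds for the adverse-event component of the tolerability and acceptability outcome. The plan compares only protocol-related events between arms, leaves relatedness undefined and unmasked, and names symptoms for a daily exposure that one arm has. Followed as written, it can turn equal event rates into unequal counts.

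The size cannot be known from the documents. Over the assumed grid, the false-difference probability runs from about 2% with equal attribution to 83% in the most extreme case. A mild imbalance (80% against 60%) gives 2.6 to 10.0%. A fourfold ratio, such as 16% against 4% (0.20 × 0.80 against 0.20 × 0.20), is tempting as a headline. It needs the most extreme attribution split tried, and even then a significant result at 30 per arm has a probability of only 14.6%. It should not be read as the expected effect.

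These figures assume one count per participant, attribution independent between participants, and Fisher's test. This is a worthwhile, cheap improvement to a rule prone to bias; it does not undermine the tolerability assessment as a whole.

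**What to change.** In Primary Outcomes (IV.A) and Intervention Acceptability (IV.C), define the between-arm adverse-event comparison as the number of participants with any adverse event regardless of relatedness. Show it also by CTCAE grade, over all randomised participants, with the risk difference and 95% CI. Keep protocol-related events as a secondary descriptive line, and state who judges relatedness and by what criteria.

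Ask about adverse events with the same questions on the same schedule in both arms, using the group meetings already planned (weekly in weeks 1-12, then monthly). This is needed because Protection against Risk (IV.D) states a weekly evaluation of tolerance for TRF+RCD only. The weekly contact described for the behavioral program covers both arms but does not mention tolerance. An all-event count would remove the attribution problem but inherit any difference in how events are asked about.

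The cost is wording, a common set of questions and one table; the events are already to be reported and graded. Sample size need not change, since no power is claimed for adverse events. Unrelated illnesses add some noise, and the interval will be wide. At 40% in both arms its half-width is about 1.96 × √(2 × 0.40 × 0.60 / 30) = 0.25, or 25 percentage points, so the result should be read as an estimate rather than a test.

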Adherence: Adherence to the prescribed study diet will be objectively assessed through review of meal logs collected with the MealLogger app and Google Voice account as described above, as well as through evaluation of glucose excursions in comparison with the meal logs in order to determine if glucose excursions exist in absence of recorded food intake. In addition, adherence will be assessed subjectively as described above through the use of questionnaires using Likert scales to address ability to adhere to the study diet.

Post-intervention assessments. Within 3 weeks following the initial 12-week weight loss intervention all participants will complete 7 days of free-living EI recording (cell phone app), PA recording (accelerometers), sleep recording (wrist actigraph), appetite recording (VAS), and glucose monitoring (CGM) as described above for the baseline assessments. Participants will also have repeat assessments of HgbA1c, lipid panel, resting metabolic rate and body composition (DXA) during an outpatient CTRC visit. Participants will also repeat questionnaires as described above: adherence to the dietary intervention, QOL (RAND-36), mood state (POMS-2), eating behaviors (TFEQ), and sleep questionnaires (Berlin Questionnaire, Epworth Sleepiness Scale, Pittsburgh Sleep Quality Index, and Morningness -Eveningness Questionnaire). Participants completing the optional in-laboratory room calorimeter and objective sleep measurements at baseline will be asked to complete follow-up measurements. The follow-up measurements of sleep and nocturnal energy metabolism can be completed on any evening starting at week 10 of the intervention not to exceed 4 weeks following completion of the intervention. The only exception is that the inpatient visit cannot occur during the 7 days of free-living EI, PA, and glucose monitoring.

COVID-19 Post Intervention Changes

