Due to the COVID-19 pandemic, we are unable to carry out week 12 measures as described above. Instead, the study team will drop off the accelerometer and wrist actigraph to participant's homes. The packet of devices will be left on the participant's doorstep to eliminate person to person contact. Proper PPE will be worn by the study team during the drop-off and pick-up time including gloves and masks. The participants will be asked to wait a few days before wearing the devices and encouraged to wipe each device down before placing it back in the packet for pick-up. Once the participants have worn the device for 7 consecutive days, the study team will pick up the devices from the doorstep and wipe down the packet with a disinfecting wipe. The devices will not be handled by the study team for at least 1 week post pick-up. The devices will be handled as follows:

- The study team will wear gloves and a mask any time they are handling devices
- Devices will be disinfected with a Cavi-wipe before being placed in the individual device packets
- Each device will be placed in its own sanitized plastic bag before being placed in the device packet
- Devices will be given to the entire cohort on one date, so that there will be no sharing of devices between participants
- No study team member will handle devices if they are exhibiting symptoms of COVID-19 or have been exposed in the last 14 days.

These measures will be put into place so long as the orders from campus, local, state, or federal government are such that the study measures cannot be carried out as originally planned. The study team will resume normal visit procedures once it is safe and permitted to do so.

We will still collect all non-contact outcomes such as the appetite recording (VAS), and the 7 days of food logging via Google voice. In addition to these measures, for the cohort participating in the weight loss intervention during the COVID-19 pandemic only, we will administer a questionnaire specific to COVID-19 (changes in work, levels of motivation, ability to adhere to the diet, etc) as well as the Perceived Stress Scale, a validated psychological instrument for measuring the perception of stress. CTRC measures such as the DXA, blood panel, and resting metabolic rate will not be collected under these circumstances.

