Statistical Analysis: Efficacy Testing: Baseline demographic characteristics will be summarized by treatment groups using descriptive statistics. Any imbalance between groups will be examined using two-sample t-tests and Fisher's exact tests as appropriate. The primary analysis will use the ITT principle to test our study hypotheses under practical and realistic conditions when not all participants follow or complete the program. All randomized participants will be analyzed. A linear mixed effect model (LMM) will serve as the primary method to handle missing values. The normality assumptions will be evaluated and transformations used (e.g. square root and log) as appropriate. Change in weight is the primary outcome variable and others will be secondary outcomes. Consequently, no adjustment for multiple outcomes will be applied. P-values <0.05 will be considered significant. No interim analysis is planned. Any imbalance in baseline characteristics between groups that could potentially be a confounding factor for the outcome will be adjusted for in the statistical model (i.e., age, sex, level of PA achieved during intervention). Differences between groups in weight, fat mass, lean mass, MVPA, EI, sleep outcomes, and glucose variability will be compared using a LMM. Specifically, the test of time by group interaction will be used to assess efficacy. Pearson's correlations will be used to assess the relationship between sleep and nocturnal metabolism outcomes and longitudinal weight regain at 6 months. Variability of Major

Outcome Measures: Standard deviation and effect sizes will be determined based on the LMM model estimates to assist with planning the large-scale trial.

G. Summarize Knowledge to be Gained:

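### The COVID-19 week-12 procedure gives no method for a 12-week weight and no CGM, so both appear uncollected for the whole affected cohort, and the analysis plan does not say how the gap is handled.

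*Combined protocol and SAP*

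**What the plan says.** The ordinary post-intervention assessments in section IV.C include, after week 12, "appetite recording (VAS), and glucose monitoring (CGM) as described above for the baseline assessments". The COVID-19 subsection replaces them with a doorstep delivery: "we are unable to carry out week 12 measures as described above. Instead, the study team will drop off the accelerometer and wrist actigraph". It keeps some measures, "We will still collect all non-contact outcomes such as the appetite recording (VAS), and the 7 days of food logging via Google voice", and adds a COVID-19 questionnaire and a stress scale. It drops others: "CTRC measures such as the DXA, blood panel, and resting metabolic rate will not be collected under these circumstances". The procedure is cohort-wide ("Devices will be given to the entire cohort on one date") and conditional ("The study team will resume normal visit procedures once it is safe and permitted to do so").

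Section IV.A requires a scale weight at 12 weeks, and the baseline section specifies a digital scale. No home or self-reported weight is described anywhere. Section IV.A also makes adherence a primary outcome, assessed by self-report and "with the use of a smartphone application in conjunction with continuous glucose monitoring". Section IV.E places CGM at baseline and 12 weeks only.

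In section IV.F the sample size is based on 12-week weight change, and the analysis text states: "Change in weight is the primary outcome variable and others will be secondary outcomes". Missing values are left to a linear mixed model (LMM), with no provision for a time point missing across a whole cohort.

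**The concern.** Two measurements that the plan depends on have no stated route in the affected cohort.

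- **Weight.** If no 12-week weight is taken, the 12-week contrast rests on the other cohorts, and the LMM supplies this cohort's 12-week value by model alone. Weight regain from week 12 to the 6-month follow-up, part of Aim 1b, could not be observed there. The variability and effect-size estimates that Aim 1b is meant to deliver would be less precise.
- **CGM.** Its role is to reveal eating that was not logged. Week 12 is its only use after baseline, so without it this cohort's logs have no such check and adherence is measured differently across cohorts.

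There is a side effect on feasibility. Section IV.F ties modification of the intervention to completing outcome measures on time in more than 90% of participants. A cohort of 10% or more without a given week-12 measure puts that threshold out of reach for that measure, for reasons unrelated to the intervention.

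**Working it through.** **Inputs (section IV.F).** 60 recruited, 20% attrition, 48 completers, 24 per arm; alpha 0.05 (taken as two-sided); SD 3.7 kg for RCD and 4.2 kg for RCD+TRF; stated detectable difference 3.5 kg at 80% power.

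**Formula.** SE = √[(3.7² + 4.2²)/n] = √(31.33/n), with n per arm. Power comes from the noncentral t with 2n − 2 degrees of freedom and noncentrality (difference/SE). The detectable difference is the value that gives 80% power.

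**The plan's own figure.** At n = 24, SE = √(31.33/24) = 1.14 kg. The detectable difference is 3.27 kg, and power at 3.5 kg is 85%. The stated 3.5 kg is therefore somewhat conservative. With SD 4.2 in both arms the result is 3.47 kg and 81%, which matches it.

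**Without the affected cohort's 12-week weights.** Its size is not given, so its share f is an assumption; n = 24(1 − f).

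| Assumed share | n per arm | SE (kg) | Detectable difference (kg) | Power at 3.5 kg | Same, SD 4.2 in both arms |
|---|---|---|---|---|---|
| none | 24 | 1.14 | 3.27 | 85% | 3.47 kg, 81% |
| 1/4 | 18 | 1.32 | 3.80 | 73% | 4.04 kg, 68% |
| 1/3 | 16 | 1.40 | 4.05 | 68% | 4.30 kg, 63% |
| 1/2 | 12 | 1.62 | 4.74 | 54% | 5.03 kg, 50% |

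**What the 6-month weights could recover.** The table is a complete-case calculation, whereas the plan uses an LMM. Suppose everyone has the 6-month weight, and its change correlates ρ with the 12-week change. In a large-sample approximation the detectable difference is 3.27 × √[(1 − ρ²f)/(1 − f)]. At f = 1/3:

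- ρ = 0.5: 3.27 × √(0.917/0.667) = 3.83 kg
- ρ = 0.8: 3.27 × √(0.787/0.667) = 3.55 kg

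Both correlations are assumed; the documents give none. Part of the loss is recovered, but not all of it.

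**The 90% criterion.** With share f unmeasured, at most 1 − f of participants have the measure: 75%, 67% or 50% for the shares above. Any f of 10% or more rules out exceeding 90%.

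**The case against.** A reader might infer that the 12-week weight is definitely lost. The text does not say so. The list of retained measures and the list of dropped ones are both open-ended, neither names weight, and a home weight would fit among the non-contact outcomes. The ordinary week-12 list does not name scale weight either, although section IV.A requires it, so silence in the COVID-19 text is weak evidence. The inference is firmer for CGM, which is a device that is absent from the packet.

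A reader might also infer that adherence as a whole is lost. It is not. Meal logs are the record and CGM the cross-check. The week-12 log is expressly kept, and logs at weeks 4 and 8 and monthly in months 4 to 9 continue, as do the self-ratings.

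The power loss should not be overplayed. Aim 1b already says the pilot lacks power for weight differences, and section IV.A lists weight as secondary, in conflict with section IV.F. The table's figures are worst cases. The 1/2 share is the extreme: the meal-logging text implies that the affected cohort followed Cohorts 1 and 2 (section IV.F plans only two cohorts), so it would have to equal all earlier cohorts combined. An administrative gap that affects both arms gives no evident reason for bias.

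These points limit the size of the concern. What remains is that no method for a 12-week weight is stated, CGM is missing from the packet, and section IV.F is silent on both.

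**Conclusion.** The point holds as a gap in specification with a cost mainly in precision. As written, the affected cohort has no stated route to a 12-week weight or to CGM, so both appear uncollected while the procedure is in force.

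For an assumed share of 1/4 to 1/2 of the 48 completers, the complete-case detectable difference rises from 3.27 kg to about 3.8–4.7 kg, and power at 3.5 kg falls from 85% to about 73%–54%. This rests on the plan's SDs, a two-sided test, equal loss in both arms and no gain from baseline adjustment or later weights; the true cost is probably smaller. For adherence, what goes is CGM verification in one cohort, not the outcome itself. Regain from week 12 would be unobservable in that cohort.

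**What to change.** 1. Wherever the COVID-19 procedure applies, obtain a 12-week home weight, either with a scale in the packet already being delivered or with a weight verified by photo or over Zoom. Record the measurement mode, include cohort and mode in the LMM, and add a sensitivity analysis that excludes remote weights.
2. If that window has passed (this version already refers to the mid-intervention switch to Zoom as done), state whether any 12-week weight was obtained. If none was, report the 12-week contrast as resting on the cohorts measured in person and restate the detectable difference with the actual numbers.
3. Keep CGM-verified adherence where CGM was worn. Add a log-only adherence analysis, common to all cohorts, as a sensitivity analysis. Replacing the primary measure with logs everywhere would discard valid CGM data and is not needed.
4. State that measures suspended by public-health orders do not count as failures of the 90% criterion.

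The cost is some scales or a few minutes of an existing Zoom contact, slightly noisier weights, and a short addition to section IV.F. Items 2 to 4 need only text and analysis.
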